#### 9.3.2.3.4 Serious Adverse Events

Information on SAEs will be collected and assessed throughout the trial, from Visit 1 until 180 days after vaccination.

Any SAE occurring at any time during the trial will be reported by the Investigator through the EDC system and according to the completion guidelines provided by the Sponsor. All information concerning the SAE is to be reported, either as part of the initial reporting or during follow-up reporting if relevant information became available later (e.g., outcome, medical history, results of investigations, copy of hospitalization reports). The Investigator will assess the causal relationship between the SAE and the investigational product as either “Not related” or “Related”, as described in [Section 10.4](#).

See [Section 10](#) for further details on SAE reporting.

#### 9.3.2.3.5 Adverse Events of Special Interest

Not applicable.

#### 9.3.2.3.6 Medically-Attended Adverse Events

MAAE information will be collected throughout the study. MAAEs that occur from Visit 1 (D0) to Visit 2 (D30[+14days]) will be recorded as unsolicited AEs on the diary card as part of all unsolicited AEs collected for this post-vaccination period. MAAEs that occur from Visit 2 (D30 [+14 days]) to D180 (+14 days) will be recorded as such in the MA. An MAAE that occurs within the study period but meets the definition of an SAE should be reported only on the SAE Reporting Form, but not on the MAAE page of the CRF. The Investigator will assess the causal relationship between the MAAE and the investigational or study product as either “not related” or “Related,” as described in [Section 9.3.2.3.7](#).

#### 9.3.2.3.7 Assessment of Causality

The Investigator will assess the *causal relationship* between each unsolicited systemic AE and vaccination as either not related or related, based on the following definitionsa:

- 0: Not related – The AE is clearly / most probably caused by other etiologies such as subject’s underlying condition, therapeutic intervention, or concomitant therapy; or the delay between vaccination and the onset of the AE is incompatible with a causal relationship; or the AE started before the vaccination (screening phase, if applicable)
- 1: Related – There is a “reasonable possibility” that the AE was caused by the vaccination, meaning that there is evidence or arguments to suggest a causal relationship

---

a ICH Guidelines, Clinical Safety Data Management E2A

Note: By convention, all injection site AEs (solicited and unsolicited) and all solicited systemic reactions are considered to be related to vaccination and referred to as reactions, and therefore do not require the Investigator’s opinion on relatedness.

AEs likely to be related to the product, whether serious or not, that persist at the end of the trial will be followed up by the Investigator until their complete disappearance or the stabilization of the subject’s condition. The Investigator will inform the Sponsor of the date of final disappearance of the event.

### 9.3.3 Efficacy

No clinical efficacy data will be obtained in the trial.

## 10 Reporting of Serious Adverse Events

In order to comply with current regulations on SAE reporting to health authorities, the Investigator must document all SAEs regardless of causal relationship, and notify the Sponsor and the Clinical Research Associate (CRA) within the notification timelines stated in the following sections. The Investigator will give access and provide the Sponsor and the CRA with all necessary information to allow the Sponsor to conduct a detailed analysis of the safety of the investigational product. It is the responsibility of the Investigator to request all necessary documentation (e.g., medical records, discharge summary, autopsy) in order to provide comprehensive safety information. All relevant information must then be transcribed into the electronic Serious Adverse Events (eSAE) Form.

### 10.1 Initial Reporting by the Investigator

SAEs occurring during a subject’s participation in the trial or experiment must be reported within 24 hours to the Sponsor’s GPV Department and to the CRA. Every SAE must be reported, even if the Investigator considers that it is not related to the vaccine. The SAE form must be signed by a licensed physician (M.D. or D.O.) for whom the task is listed on the Study Task Delegation and Signature List after each update to the Form.

The Investigator must complete the “eSAE Form” in the EDC application. After validation, an e-mail alert will automatically be sent to the GPV mailbox, the CRA and the Clinical Team Leader (CTL). This message will include the country, the study code, the subject number, whether the report is initial or a follow-up, the diagnosis and / or symptoms, the seriousness criteria, the relationship, if related and the outcome, if fatal.

If the EDC system is unavailable, the site must notify the Sponsor using the paper version of the SAE Reporting Form, as follows:

The Investigator must complete the SAE Reporting Form, check off the “Initial Reporting Form” box, and send it to the Sponsor by one of the following means (preferably by fax or email):

- By fax, to the following number: [REDACTED]

- In PDF format to the following e-mail address, using a method of transmission that includes password protection: [REDACTED] (see the Operating Guidelines for directions on how to send a password protected email).
- By express mail, to the following address:  
Sanofi Pasteur Inc.  
Reception and Triage – Case Management  
Global PharmacoVigilance  
[name]  
[name]  
[name]

When the system becomes available, the Investigator must transcribe the information from the paper version of the eSAE Form into the EDC system.

If there is need for urgent consultation, the Investigator is to contact the RMO. If the RMO cannot be reached, the Investigator may contact the Call Center as described in [Section 5.3](#).

## 10.2 Follow-up Reporting by the Investigator

The eSAE Form completed initially must be updated within 24 hours after the Investigator has become aware of any new relevant information concerning the SAE (e.g., outcome, precise description of medical history, results of the investigation). After validation, an e-mail alert will be sent automatically to the GPV Department and to the CRA. All relevant information must be included directly in the eSAE Form. Copies of documents (e.g., medical records, discharge summary, autopsy) may be requested by the GPV Department.

The anonymity of the subject must always be respected when forwarding this information.

## 10.3 Reporting of SAEs Occurring After a Subject Has Completed the Study

Any SAE that occurs after a subject has completed the study but that is likely to be related to the product or to the experiment must also be reported as soon as possible. In such a case, the reporting procedure to be followed is identical to that described in [Section 10.1](#).

## 10.4 Assessment of Causality

The causal relationship between the SAE and the product will first be evaluated by the Investigator, using the following definitions:

**0 - Not related:** The AE is clearly / most probably caused by other etiologies such as an underlying condition, therapeutic intervention, or concomitant therapy; or the delay between vaccination and the onset of the SAE is incompatible with a causal relationship; or the SAE started before the vaccination (screening phase, if applicable).

**1 - Related:** There is a “reasonable possibility” that the SAE was caused by the vaccination, meaning that there is evidence or arguments to suggest a causal relationship.

*(ICH Guidelines, Clinical Safety Data Management E2A)*

Following this, the Sponsor's Product Safety Officer (PSO) will also assess the causal relationship to the product, based on the available information and current medical knowledge.

The decision to modify or discontinue the trial may be made after mutual agreement between the Sponsor and the Investigator(s).

## 10.5 Reporting SAEs to Health Authorities and IECs / IRBs

The Sponsor will inform the relevant health authorities of any reportable SAEs according to the local regulatory requirements. Reporting to the health authorities will be according to the Sponsor's standard operating procedures.

The Sponsor's RMO, [REDACTED], [REDACTED], [REDACTED] will notify the Investigators in writing of the occurrence of any reportable SAEs. The Investigators / Sponsor will be responsible for informing the IECs or IRBs that reviewed the trial protocol.

## 11 Data Collection and Management

### 11.1 Data Collection and CRF Completion

Individual safety DCs, specifically designed for this trial by the Sponsor and provided to the study sites, will be given to study participants for the recording of daily safety information as described in [Section 9.3.2.3](#). The DCs will include prelisted terms and intensity scales (see [Table 9.1](#) and [Table 9.2](#)) as well as areas for free text to capture additional safety information or other relevant details. Subjects will also be provided with rulers for measuring the size of injection site reactions, and with standard digital thermometers for measuring daily temperatures. To ensure consistency of reporting, the study sites will instruct subjects on how to correctly use these tools.

The 6-month follow-up will be done by interviewing subjects either during a visit or over the telephone using a questionnaire to capture SAEs and AEs of particular interest, if applicable. An MA will be provided to the subjects at the preceding trial visit to help them record information on events occurring between this visit and the 6-month follow-up.

Relevant information will be transcribed into the CRF. Any SAEs captured during this 6-month follow-up period will be reported and followed-up as per the normal process for reporting SAEs.

The clinical team may decide to replace the MA by a diary card if a follow-up visit is planned for the subjects.

At specified intervals, the Investigator or an authorized designee will interview the subjects to collect the information recorded in the diary card, and will attempt to clarify anything that is incomplete or unclear. All clinical trial information gathered by the study site will be reported electronically by the Investigator or authorized designee using a web-based CRF. (Any information that was not documented in the diary card will first be captured in the source document and then reported electronically.) The CRF has been designed specifically for this trial under the responsibility of the Sponsor, using a validated Electronic Records / Electronic Signature-compliant platform (21 CFR Part 11).

To ensure the correct and consistent completion of the CRFs, the Sponsor or authorized representative will provide all necessary tools, instructions, and training to all site staff involved in data entry prior to study start. Additional instructional documents such as training manuals and completion guidelines will be provided to assist with data entry during the course of the trial.

Upon completion of training, each user requiring access to the EDC system will be issued a unique username and password. In the event of a change in trial personnel, each newly assigned individual will receive a unique username and password; the username and password of a previous user may not be reissued. If any trial personnel leave the study, the Investigator is responsible for informing the Sponsor immediately so that their access is deactivated. An audit trail will be initiated in the EDC system at the time of the first data entry in order to track all modifications and to ensure database integrity.

The Investigator is responsible for the timeliness, completeness, and accuracy of the information in the CRFs; must provide explanations for all missing information; and must sign the CRF using an e-signature.

## 11.2 Data Management

### *Management of Clinical Data*

Data generated during the trial will be managed following two different processes:

- Clinical data, defined as all data reported in the CRF, and laboratory data will be handled by the Sponsor's Clinical Data Management (CDM) platform or authorized representative.
- Data pertaining to SAEs, which are reported by the Investigator on the eSAE Forms or SAE Reporting Forms, will be handled by the Sponsor's GPV Department.

During the trial, clinical data reported in the CRFs will be integrated into the clinical database under the responsibility of the Sanofi Pasteur CDM platform. Data monitoring at the sites and quality control in the form of computerized logic and / or consistency checks will be systematically applied in order to detect errors or omissions. In addition, data reviews may be performed several times by the Sponsor's staff in the course of the trial. Any questions pertaining to the reported clinical data will be submitted to the investigator for resolution using the EDC system. Each step of this process will be monitored through the implementation of individual passwords to maintain appropriate database access and to ensure database integrity.

The validation of the immunogenicity data will be performed at the laboratory level following the laboratory's procedures. Information from the laboratory will be checked for consistency before integration into the clinical database.

After integration of all corrections in the complete set of data, and after the SAE information available from CDM and the GPV Department has been reconciled, the database will be released for statistical analysis.

### ***SAE Data Management***

During the trial, data pertaining to SAEs reported on eSAE Forms will be integrated into the Sponsor's centralized GPV database.

Upon receipt of an eSAE Form, the data will be entered into the GPV database after a duplicate check. Each SAE case will be assigned a case identification number. Each case will be entered in the GPV database and assessed by the case management platform or its delegate before being reported to the relevant authorities as necessary. Assessment of related cases will be done in collaboration with the PSO and the RMO. Follow-up information concerning a completed case will be entered into the GPV database, and a new version of the case will be created.

The information pertaining to SAEs in the GPV database will be reconciled with that in the clinical database.

### **11.3 Data Review**

A review of the data is anticipated through the data review process led by Data Management before database lock.

The safety of the investigational product will be continuously monitored by the Sponsor. Periodic safety data review will be performed by the Sponsor's Safety Management Team (SMT). For all periodic safety reviews, blinded safety data will be provided to the Sponsor's SMT.

## **12 Statistical Methods and Determination of Sample Size**

### **12.1 Statistical Methods**

Clinical data will be analyzed under the responsibility of the Biostatistics Platform of the Sponsor. A statistical analysis plan (SAP) will be written and peer reviewed before any analyses. In accordance with the protocol, the SAP will describe all analyses to be performed under the responsibility of the Sponsor and all the conventions to be taken.

#### **12.1.1 Hypotheses and Statistical Methods for Primary Objective**

Thirty days after the administration of MenACYW conjugate vaccine or Menomune® – A/C/Y/W-135, the percentages of subjects who achieve an hSBA vaccine seroresponsea for meningococcal serogroups A, C, Y, and W in Group 1 are non-inferior to the corresponding percentages in Group 2.

Null hypothesis ( $H_0$ ):  $p(G_1) - p(G_2) \leq -10\%$

---

a hSBA vaccine seroresponse for serogroups A, C, Y, and W is defined as:

- For a subject with a pre-vaccination titer < 1:8, the post-vaccination titer must be  $\geq 1:16$ .
- For a subject with a pre-vaccination titer  $\geq 1:8$ , the post-vaccination titer must be at least 4-fold greater than the pre-vaccination titer.

Alternative hypothesis ( $H_1$ ):  $p_{(G1)} - p_{(G2)} > -10\%$

where  $p_{(G1)}$  and  $p_{(G2)}$  are the percentages of subjects who achieve an hSBA seroresponse in Group 1 and Group 2, respectively. Each of the serogroups A, C, Y, and W will be tested separately. If the lower limit of the 2-sided 95% confidence interval (CI) of the difference between the 2 proportions is  $> -10\%$ , the inferiority assumption will be rejected.

For the 4 non-inferiority hypotheses using the seroresponse rates, the CI of the difference in proportions will be computed using the Wilson Score method without continuity correction (33). The overall non-inferiority of this objective will be demonstrated if all 4 individual null hypotheses are rejected.

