## 5 Investigational Plan

### 5.1 Description of the Overall Trial Design and Plan

#### 5.1.1 Trial Design

This is a Phase III modified double-blind, randomized, parallel-group, active-controlled, multi-center trial to compare the immunogenicity and safety of MenACYW conjugate vaccine to Menomune® - A/C/Y/W-135 in adults  $\geq 56$  years of age in the US.

Approximately 900 healthy adults will be randomized in a 1:1 ratio to the following groups:

- Group 1: MenACYW conjugate vaccine
- Group 2: Menomune® - A/C/Y/W-135

Enrollment will be stratified by age (see [Table 5.1](#)).

For subjects 56 to 64 years of age, 200 subjects will be enrolled in both Group 1 and Group 2.

For subjects 65 years of age and older, 250 subjects will be enrolled in both Group 1 and Group 2. These subjects will be further stratified into 2 groups as 65 to 74 years of age and 75 years of age and older. At least 25% of the 250 subjects will be enrolled in each of these age groups.

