### 12.2.4 Populations Used in Analyses

All immunogenicity analyses will be performed on the PPAS. Additional immunogenicity analyses will be performed for exploratory purposes on the FAS according to randomization group. All safety analyses will be performed on the SafAS. Subjects will be analyzed according to the vaccine they actually received.

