3.1 Trial Design

This is a Phase III modified double-blind, randomized, parallel-group, active-controlled, multi-center trial to compare the immunogenicity and safety of MenACYW conjugate vaccine to Menomune[®] – A/C/Y/W-135 in adults ≥ 56 years of age in the US.

Approximately 900 healthy adults will be randomized in a 1:1 ratio to the following groups:

- Group 1: MenACYW conjugate vaccine
- Group 2: Menomune[®] – A/C/Y/W-135

Enrollment will be stratified by age (see Table 3.1).

For subjects 56 to 64 years of age, 200 subjects will be enrolled in both Group 1 and Group 2.

For subjects 65 years of age and older, 250 subjects will be enrolled in both Group 1 and Group 2. These subjects will be further stratified into 2 groups as 65 to 74 years of age and 75 years of age and older. At least 25% of the 250 subjects will be enrolled in each of these age groups.

Table 3.1: Testing strategy for *N. meningitidis* serogroups ACYW

	ACYW serogroups tested by hSBA (all subjects)	ACYW serogroups tested by rSBA (subset)
Group 1		
56-64 years	200	50
≥ 65 years:	250	50
65-74 years	70-180	15-35
≥ 75 years	70-180	15-35
Group 2		
56-64 years	200	50
≥ 65 years:	250	50
65-74 years	70-180	15-35
≥ 75 years	70-180	15-35

All subjects will provide pre-vaccination blood samples for immunogenicity assessment at baseline (Visit 1) and at Day (D)30 (+14-day window) post-vaccination (Visit 2). Solicited AE information will be collected for 7 days after vaccination, unsolicited AE information will be collected from Visit 1 to D30 (Visit 2), and SAE information will be collected from D0 through D180 (+14 days) after vaccination. Information on medically-attended adverse events (MAAEs) will be collected from Visit 1 through Visit 2 (as part of the collection of unsolicited AE information) and from Visit 2 through D180 (+14 days) (as MAAEs).

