5.1.1.2 Statistical Methods

Each of the serogroups A, C, Y, and W will be tested separately. If the lower limit of the 2-sided 95% CI of the difference between the 2 proportions is $> -10\%$, the inferiority assumption will be rejected. For the 4 non-inferiority hypotheses using the seroresponse rates, the CI of the difference in proportions ($p_1 - p_2$) will be computed using the Wilson Score method without continuity correction (7).

Let $\hat{\theta} = p_1 - p_2$, then $L = \hat{\theta} - \delta$ and $U = \hat{\theta} + \varepsilon$ are respectively the lower and the upper limits of the CI, where:

$$\delta = Z_{0.025} \sqrt{\left\{ \frac{l_1(1-l_1)}{n_1} + \frac{u_2(1-u_2)}{n_2} \right\}}$$

$$\varepsilon = Z_{0.025} \sqrt{\left\{ \frac{l_2(1-l_2)}{n_2} + \frac{u_1(1-u_1)}{n_1} \right\}}$$

l_1 and u_1 are calculated from the CI of the single proportion in Group 1 given by:

$$\frac{(2n_1p_1 + Z_{0.025}^2 \pm Z_{0.025} \sqrt{(Z_{0.025}^2 + 4n_1p_1(1-p_1))})}{2(n_1 + Z_{0.025}^2)}$$

l_2 and u_2 are calculated from the CI of the single proportion in Group 2 given by:

$$\frac{(2n_2p_2 + Z_{0.025}^2 \pm Z_{0.025} \sqrt{(Z_{0.025}^2 + 4n_2p_2(1-p_2))})}{2(n_2 + Z_{0.025}^2)}$$

where $Z_{0.025}$ is the upper 97.5th percentile of the standard normal distribution.

The overall non-inferiority of this objective will be demonstrated if all 4 individual null hypotheses are rejected.

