5.1.4 Complementary Output

Additional analyses by age group, gender and race will be provided in Appendix 15 of the CSR.

Immunogenicity analyses:

- hSBA GMTs and 95% CI – Per-Protocol Analysis Set
- Percentage of subjects with hSBA vaccine seroresponse^a and 95% CI – Per-Protocol Analysis Set

^a hSBA vaccine seroresponse for serogroups A, C, Y, and W is defined as:

- For a subject with a pre-vaccination titer < 1:8, the post-vaccination titer must be ≥ 1:16.
- For a subject with a pre-vaccination titer ≥ 1:8, the post-vaccination titer must be at least 4-fold greater than the pre-vaccination titer.

Safety analyses:

- Safety overview after injection –Safety Analysis Set

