5.2.2 Per-Protocol Analysis Set

The PPAS is a subset of the FAS. The subjects presenting with at least 1 of the following relevant protocol deviations will be excluded from the PPAS:

- Subject did not meet all protocol-specified inclusion criteria or met at least one of the protocol-specified exclusion criteria
- Subject did not receive vaccine
- Subject received a vaccine other than the one that he / she was randomized to receive
- Preparation and / or administration of vaccine was not done as per-protocol
- Subject did not provide post-dose serology sample in the specified time window or a post-dose serology sample was not drawn. Time windows will be defined as D30 to D44 (D30 +14 days) post vaccination.
- Subject received a protocol-prohibited Category 2 or Category 3 therapy / medication / vaccine
- Subject's serology sample did not produce a valid test result
- Subject had other protocol violations that affected the subject's immune response, as determined by the clinical team before locking the database.

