5.2.5 Populations Used in Analyses

All immunogenicity analyses will be performed on the PPAS. Additional immunogenicity analyses will be performed for exploratory purposes on the FAS. In the FAS, subjects will be analyzed by the vaccine group to which they were randomized.

All safety analyses will be performed on the SafAS. Subjects will be analyzed according to the vaccine they actually received.

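### Enrolment is stratified by age but the primary interval pools all ages; a stratified Newcombe interval is a minor improvement, and the planned interval is not an error

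*Protocol*

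**What the plan says.** **Design.** Protocol 5.1.1 fixes numbers by age: "For subjects 56 to 64 years of age, 200 subjects will be enrolled in both Group 1 and Group 2". It sets 250 per group at 65 and over, split into 65-74 and 75 and over with at least 25% in each; Table 5.1 shows 70-180 per group in each of these bands. SAP 3.1 repeats this: "Enrollment will be stratified by age (see Table 3.1".

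**Primary analysis.** Protocol 12.1.1 states that "the CI of the difference in proportions will be computed using the Wilson Score method without continuity correction". The formula in SAP 5.1.1.2 takes p1, p2, n1 and n2 for whole groups and has no stratum index or weight. Each serogroup is tested against -10%, and all four must pass.

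**Age in the analysis.** SAP 5.1.4 says "Additional analyses by age group, gender and race will be provided in Appendix 15 of the CSR". For seroresponse it lists percentages with 95% CIs, and no between-group difference by age or adjusted for age.

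**Populations.** The primary analysis uses the per-protocol set (PPAS). One of its exclusions reads "Subject did not provide post-dose serology sample in the specified time window or a post-dose serology sample was not drawn". Protocol 12.2.4 adds: "Additional immunogenicity analyses will be performed for exploratory purposes on the FAS according to randomization group".

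**Not visible.** Protocol 6.5 leaves allocation details to the Operating Guidelines. SAP 5.7, on changes to planned analyses, is in the contents list but not in the text available.

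**The concern.** Equal age composition at enrolment does not guarantee equal age composition in the PPAS, which drops subjects after randomization. The Protocol synopsis itself expects 382 evaluable of 450 per group. If seroresponse depends on age, and the exclusions leave one group younger than the other, the pooled difference mixes the vaccine effect with the difference in age mix.

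A shift towards Group 1 raises the one-sided error above the nominal 2.5%. A shift towards Group 2 costs power, and with four serogroups all required to pass, any such loss matters. Comparing within the age bands that the design already uses removes this shift.

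**Working it through.** **Inputs from the documents.** 200 and 250 enrolled per group (Protocol 5.1.1); 382 of 450 evaluable (synopsis), which is 84.9%, or about 15% loss; margin -10 points; lower limit of a two-sided 95% CI. The planning rates and power are redacted, so the plan's own power cannot be reproduced.

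**Assumptions.** Group 2 mean response 60%. Rates at 56-64 / 65-74 / 75 and over: 62.5/60/57.5, 65/60/55 and 70/60/50% for age spreads of 5, 10 and 20 points. The band of 65 and over is split evenly. The true difference is the same in every band: -10 points for error, 0 for power. Success means a lower limit above -10%.

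**Stratified Newcombe interval.** For bands s and groups i, with z = Z0.025:

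- w_s = n1s·n2s/(n1s+n2s); W_s = w_s/Σw; d = Σ W_s(p1s − p2s)
- h_is = √[p_is(1−p_is)/n_is + z²/(4n_is²)] / (1 + z²/n_is)
- z_i = z·√(Σ W_s²h_is²) / Σ(W_s h_is)
- l_is, u_is = the SAP's Wilson limits for p_is, with z_i in place of Z0.025
- L_i = Σ W_s l_is; U_i = Σ W_s u_is; k_i = Σ W_s²/n_is
- Lower = d − z√[k1·L1(1−L1) + k2·U2(1−U2)]
- Upper = d + z√[k2·L2(1−L2) + k1·U1(1−U1)]

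With one stratum this is the SAP formula. Check: 200/382 against 230/382 gives -14.78% to -0.82% by both.

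**Equal exclusions** (170/106/106 per group). Pooled and stratified results are the same:

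| Age spread | One-sided error | Power |
|---|---|---|
| 0 | 2.57% | 80.7% |
| 10 | 2.52% | 81.3% |
| 20 | 2.35% | 82.0% |

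**Unequal exclusions.** Assume 15% at 56-64 in both groups, and 20% against 10% at 65 and over: 170/100/100 (total 370) against 170/112/113 (total 395). The 56-64 share is 170/370 = 45.9% against 170/395 = 43.0%, a gap of 2.9 points.

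Bias at the 10-point spread: (170×65 + 100×60 + 100×55)/370 = 60.95 against (170×65 + 112×60 + 113×55)/395 = 60.72, a shift of 0.22 points. The same sum gives 0.11 points at the 5-point spread and 0.45 at the 20-point spread.

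| Age spread | Pooled error, shift favours Group 1 | Pooled error, shift favours Group 2 | Stratified error, either direction | Power when shift favours Group 2, pooled / stratified |
|---|---|---|---|---|
| 5 | 2.7% | 2.4% | 2.4-2.6% | not tabulated |
| 10 | 2.9% | 2.2% | 2.4-2.6% | 79.4% / 81.4% |
| 20 | 3.2% | 1.8% | 2.4-2.6% | 78.2% / 82.0% |

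The stratified bias is 0.00 points. Simulation used 2,000,000 trials for the error and equal-exclusion power cases, and 400,000 for power with unequal exclusions.

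**Wider grid** (mean rates 12-98%, spreads 0-20 points, three splits of the older band covering 70-180). With unequal exclusions, stratified error is 2.23-2.59% and pooled error 1.44-3.36%. With equal exclusions both are 2.29-2.61%.

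**How often such a gap arises by chance.** With 15% loss unrelated to age or group, the gap in the 56-64 share has SD 1.4 points, and 2.9 points or more in either direction occurs in 3.7% of trials. This is the frequency of the imbalance, not an error rate.

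**Exploratory FAS analysis.** If it restores half of the exclusions (185/113/112 against 185/119/119), the gap is 185/410 − 185/423 = 1.4 points, and pooled error is 2.7% (10 points) or 2.8% (20 points).

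**The case against.** The strongest reply is that the plan has no defect here. The interval, margin and success rule are complete and reproducible, and the pooled interval holds its error when exclusions are unrelated to age and group. **This stands.**

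Both conditions for harm are undocumented, and the documents lean the other way. In the Phase II study (Protocol 1.2.2), titres of at least 1:8 were comparable between the two age subsets. That is a different endpoint, but it is the only age evidence shown. Subject, investigator, sponsor and laboratory are blinded (Protocol 6.4), which limits group-dependent exclusion. **This also stands**, and it keeps the point minor.

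The effect is small: at most 0.45 points against a 10-point margin. With no reason to expect either direction, the errors average near nominal; for example, (3.2 + 1.8)/2 = 2.5%. Purely random exclusion does not raise the overall error: at a 20-point spread, pooled error was 2.44%. **Both are correct.**

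Stratifying removes only the age-mix shift. Exclusions related to the response itself are untouched. If one group kept 88% of responders and 82% of non-responders at a 50% rate, its estimate would be 0.88/(0.88 + 0.82) = 51.8%, a 1.8-point shift. **This is a fair limit on the claim.**

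The choice of stratified formula also matters. A variant that combines the limits by their distance from the estimate had error up to 2.8% in equal-exclusion cases with wide age spreads. The formula above did not exceed 2.61% on the grid, so the objection calls for fixing the exact formula in advance and does not defeat the proposal.

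The FAS analysis is a partial safeguard: it restores subjects excluded for timing, medication or eligibility. It still requires a valid post-vaccination result, so missed samples stay missing.

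**Conclusion.** The concern holds as a low-end improvement. Enrolment is stratified by age, the primary interval ignores the strata, and no age-stratified difference is planned in the visible text. The pooled interval is not wrong. Under the assumed unequal exclusions, its error moves from 2.5% to about 2.9-3.2% or its power drops by about 2 to 4 points, depending on direction. The stratified interval avoids both, and matches the planned one when exclusions are equal.

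These sizes rest on assumed response rates, age spreads and exclusion patterns. Confidence is medium, because the planning rates are redacted and the allocation details and SAP 5.7 could not be read.

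**What to change.** In Protocol 12.1.1 and SAP 5.1.1.2, make the primary difference and 95% CI the stratified Newcombe interval set out in the working, over 56-64, 65-74 and 75 and over. Write the weights and formula out in full, because variants differ. Keep the -10% margin and the rule that all four serogroups must pass. Report the planned unstratified interval as a sensitivity analysis, and apply the stratified interval in the exploratory FAS analysis as well.

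Do not use the Wald form d ± 1.96√Var as primary: its error reaches 2.9-3.3% at Group 2 rates of 12-15% or 95-98%.

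If the sponsor prefers to leave the primary interval alone, pre-specifying the stratified one as a sensitivity analysis would still supply the missing age-stratified comparison.

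**Cost:** protocol and SAP text plus programming, settled before database lock. No new data are needed, and no power was lost in the cases tested (80.7% by both intervals with no age effect).
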